3.2 Primary Study Endpoints

The primary endpoints are the difference in self-reported MMAS scores at 6 months between LNG-IUS and TXA treatment and the duration of use of TXA versus LNG-IUS

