6.2 Week 4-6 Visit (For women enrolled in the LNG-IUS arm)

For women enrolled in the LNG-IUS arm, a visit will be scheduled at 4-6 weeks after placement to check for IUS strings visible at the cervix. This will serve as confirmation of position of IUS. If strings are not visible, clinical evaluation will be performed including pelvic ultrasound and/or x-ray to confirm location of IUS or expulsion.

6.3 Visit 2 / Month 3

At month 3, subjects will complete questionnaires listed in the table and receive a phone call to screen for adverse events. LNG-IUS that are expelled may be replaced one time if patient desires to continue device and the expulsion occurred within the prior 7 days. The expulsion occurred within one week and. Patient outcome would be recorded as expulsion.

6.4 Visit 3 / Month 6

At month 6, subjects will complete questionnaires listed in the table and receive a phone call to screen for adverse events.

6.5 Visit 4 / Month 9

At month 9, subjects will return for a study visit and examination. Ultrasound will be performed for size of fibroids. Laboratory testing will be completed. Subjects will complete questionnaires listed in the table and screen for adverse events and finalize study participation. Participants assigned to the LNG-IUS arm will be carefully assessed to determine if there are any contraindications to continuing therapy. Those with cavity-distorting fibroids (Type I) will be counseled regarding removal of the LNG-IUS.

7 Statistical Plan

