7.2 Statistical Methods

Descriptive Statistics

Standard descriptive statistics will be generated for measurements at baseline, 3, 6, and 9 months, including mean, median, standard deviation (SD), and interquartile range (IQR) for continuous variables and counts and percentages for categorical variables.

Handling of Missing Data

Last value carry forward (LVCF) methods will be investigated to accommodate drop-outs.

Primary Hypothesis: A user-independent medical therapy (LNG-IUS) will result in better patient reported outcomes and longer use compared to self-administered medication (TXA)

Statistical analysis: The distribution of each of the continuously scaled outcome measures (MMAS total score, PBLAC score, ferritin level, hemoglobin level, UFS-QOL scores, and Rand

SF-36 composite scores) will be graphically evaluated and logarithmic transformations will be applied if the distributions are skewed in order to obtain more normally distributed distributions. At 3, 6, and 9 months separately, each of the continuously scaled outcomes will be compared between treatment arms based on fitting separate linear regression models. In addition, separate analysis of covariance (ANOCOVA) models will be fit to compare the measures between the two treatment arms after adjusting for baseline levels. The cumulative incidence (CI) function will be used to estimate the cumulative proportion of patients by time t who have intentionally discontinued treatment due to the desire or need to stop or switch treatment, after accounting for the competing risk of LNG-IUS expulsion and censoring all other participants at their date of last follow-up or end of study. Likewise we will also estimate the CI of expulsion among the LNG-IUS treatment arm. The CI estimates for intentional discontinuation over the entire 9 months of follow-up will be compared between treatment arms using the methods developed by Gray (34). All analyses will be performed based on the intention to treat principle and calculated p-values will be based on two-sided hypothesis tests. P-values less than 0.05 will be considered statistically significant. Statistical analyses will be performed using the SAS version 9.4 software package and packages in R (Version 3.1.1).

Secondary Hypothesis 1: Large fibroid size will limit the effectiveness of LNG-IUS compared with TXA; elevated BMI predicts higher success with LNG-IUS over TXA.

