Statistical analysis: The primary event of interest is unsuccessful medical therapy, defined as the intentional discontinuation of treatment due to the desire or need to stop or switch treatment. However, the analysis is complicated by the fact that women in the LNG-IUS have a competing cause of failure, namely expulsion. Since the covariates associated with intentional discontinuation of treatment may be different from those associated with expulsion it will be important to analyze expulsion as a competing risk (35). We will first explore the associations between the covariates of interest and the competing risks by fitting separate Fine-Gray models for each type of failure using the `finegray` function in the `survival` package in R. We will also utilize the `mstate` package in R to further explore these associations. We will also explore whether the factors associated with intentional discontinuation differ between the two treatment arms.

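### Duration of use is a primary endpoint, but the only between-arm test counts intentional stopping and treats LNG-IUS expulsion as a competing event, so any-cause time on treatment is not compared and the test tilts towards LNG-IUS

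*Combined protocol and SAP*

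**What the plan says.** Section 3.2 lists two primary endpoints: MMAS at 6 months and "the duration of use of TXA versus LNG-IUS". Neither that section nor the primary hypothesis of longer use on LNG-IUS (sections 2 and 7.2) limits use by the reason it ended.

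Section 7.2 defines the analysed event as intentional discontinuation, estimated "after accounting for the competing risk of LNG-IUS expulsion and censoring all other participants at their date of last follow-up or end of study". The between-arm comparison is Gray's test: "The CI estimates for intentional discontinuation over the entire 9 months of follow-up will be compared between treatment arms". Expulsion is described in one arm only: "Likewise we will also estimate the CI of expulsion among the LNG-IUS treatment arm". Under the secondary hypothesis, the same section says that "women in the LNG-IUS have a competing cause of failure, namely expulsion".

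Section 6.3 says "LNG-IUS that are expelled may be replaced one time if patient desires to continue device", subject to a 7-day limit. An unfinished sentence follows, and then "Patient outcome would be recorded as expulsion".

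Section 7.1 gives the duration endpoint its own power statement, based on continued use at 6 months of 62% versus 22% in claims data and a chi-square test. Section 1.1 says that reasons for stopping were not available in those data.

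**The concern.** An expulsion without replacement ends use of the device. It can happen in only one arm, and the protocol itself calls it a failure, yet it is not an event in the one test that bears on duration. No other section supplies the missing comparison. Section 7.3 adds a treated population, not an endpoint, and the Fine-Gray and multi-state models in 7.2 explore predictors.

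A significant Gray test would be read as support for longer use, when it shows only less intentional stopping. If time on treatment is similar in the two arms, the result can favour LNG-IUS. If use is somewhat shorter on LNG-IUS, the test can fail to show it. The power statement concerns a third quantity, continued use whatever the reason for stopping, which is not the event tested.

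**Working it through.** **The plan's own figure.** Inputs from 7.1: 62% versus 22%, 80 per arm, two-sided 0.05. With pooled p = 0.42, SE0 = √(2·0.42·0.58/80) = 0.0780 and SE1 = √((0.62·0.38 + 0.22·0.78)/80) = 0.0713. Power = Φ((0.40 − 1.96·0.0780)/0.0713) = 99.97%. The claim of over 90% reproduces, for continued use.

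**Direction and size of the tilt.** Let e be the 9-month cumulative incidence of unreplaced expulsion as first event.

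- LNG-IUS: intentional = any-cause − e.
- TXA: intentional = any-cause.
- Tested gap (TXA − LNG-IUS) = any-cause gap + e.

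**Values of e.** The documents give no 9-month rate. Section 1.1 says up to 12%, in a sentence that ends with a 2-year time point. Read as a 2-year rate at constant hazard, 12% gives 1 − 0.88^(9/24) = 4.7% at 9 months; with half of those replaced, about 2.3%. The range used is 0 to 12%.

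**Equal any-cause use.** Assumptions: 80 per arm, exponential end of use, 50% ended by month 9 in both arms, expulsions a random share of LNG-IUS endings, and independent drop-out of 0 or 20% by month 9. Each setting had 20,000 simulated trials. Gray's test was computed with expelled women kept in the risk set to their own censoring time. The table gives the share of trials significantly favouring LNG-IUS.

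| Unreplaced expulsion | No drop-out | 20% drop-out |
|---|---|---|
| 0% | 2.6% | 2.6% |
| 2.3% | 4.6% | 4.6% |
| 3% | 6.0% | 5.7% |
| 4.7% | 8.4% | 7.9% |
| 6% | 11.0% | 10.3% |
| 9% | 20.8% | 18.0% |
| 12% | 32.8% | 29.9% |

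The any-cause log-rank test on the same data rejected, two-sided, in 4.7% to 5.4% of trials throughout. If all expulsions fall in the first 3 months (20% drop-out), the planned test favours LNG-IUS in 6.0%, 9.7%, 13.6% and 40.7% of trials at 3%, 4.7%, 6% and 12%. With 40% to 70% ended instead of 50% (no drop-out), the range is 11.0% to 11.9% at 6% expulsion and 31.9% to 35.9% at 12%.

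Hand check at 12%: intentional stopping is 50% versus 38%. SE0 = √(2·0.44·0.56/80) = 0.0785 and SE1 = √((0.25 + 0.38·0.62)/80) = 0.0779. Φ((0.12 − 1.96·0.0785)/0.0779) = 33%, in line with 32.8%.

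**Shorter use on LNG-IUS.** With 56% ended on LNG-IUS, 50% on TXA and 6% expulsion, the tested gap is 50 − (56 − 6) = 0. With 20% drop-out, the planned test finds against LNG-IUS in 2.8% of trials and the any-cause log-rank in 11.2%.

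**True LNG-IUS advantage.** With 45% versus 55% ended, 6% expulsion and no drop-out, the planned test favours LNG-IUS in 53% of trials and the any-cause log-rank in 25%.

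**Planning rates.** Extending the 6-month rates exponentially, use has ended by month 9 in 1 − 0.62^1.5 = 51.2% on LNG-IUS and 1 − 0.22^1.5 = 89.7% on TXA, a gap of 38.5 points. The tested gap is 38.5 + 3 = 41.5, 38.5 + 6 = 44.5 or 38.5 + 12 = 50.5 points. Both tests reject in about 100% of trials.

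**Replaced devices.** Suppose a replaced device is also closed out as an expulsion. With e now all expulsions, r the share replaced and s the share of those women who later stop, the tilt is e(1 − r) + e·r·s. For e = 12%, r = 50% and s = 20% to 38% (all assumed), that is 7.2 to 8.3 points, against 6 points if women with replaced devices stay at risk.

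**The case against.** The plan states its event openly, names expulsion as a competing risk, and chooses a test that fits. Time to intentional stopping is part of duration. Expulsion is also visible: it cannot occur on TXA, so a reader can add the two LNG-IUS curves. In the equal-use scenarios intentional stopping really does differ, so the rejections are correct for the hypothesis tested. The documents' own figures, including the early loss of nearly all randomised TXA participants reported in 1.1, point to a large difference, where the choice would not alter the conclusion. The 12% comes from a small sample and may be a 2-year figure. Section 7.1 names MMAS as the primary outcome variable.

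Much of this stands. The method is not wrong for its event, the high expulsion settings are extremes, and at the planned effect only the reported size changes. Three points remain. The event chosen is not the endpoint listed in 3.2 or the longer use hypothesised in 7.2. Adding two curves gives an estimate, but no test or interval on the sum is planned. MMAS being named in 7.1 does not remove duration from 3.2, and 7.1 gives duration its own power statement. The rejection rates above are errors only when the result is read as a statement about duration, but that is how the hypothesis is worded.

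**Conclusion.** The concern holds. The endpoint and its test do not match: duration of use is primary, yet no between-arm analysis of any-cause end of use is planned. The planned comparison is tilted towards LNG-IUS by the cumulative incidence of unreplaced expulsion, or by somewhat more than that if women with replaced devices are also removed from risk. With equal time on treatment, the share of trials favouring LNG-IUS rises from 2.5% to between 4.6% and 10.3% for 2.3% to 6% expulsion, and to about 30% at the protocol's upper figure of 12% (20% drop-out). These sizes rest on an assumed 9-month expulsion rate, exponential end of use and 50% ended by month 9; the direction does not depend on them. At 62% versus 22% the conclusion would survive and the size of the advantage would be overstated.

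**What to change.** In section 7.2, define duration of use and analyse it between arms as time to end of index treatment for any reason, including expulsion without replacement. Use Kaplan-Meier curves with a log-rank test or Cox model, or restricted mean months of use over 9 months. State that women who continue with a replaced device remain at risk, and reconcile this with section 6.3, where the text is incomplete. Say how removal for displacement (4.4.1) is coded, since the documents leave open whether it counts as a need to stop or as expulsion. Restate the power sentence in 7.1 for the event and test actually used. Keep Gray's test and the two cumulative incidence curves as supportive.

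The cost is SAP wording, plus dates of stopping and of expulsion if the CRF does not already hold them. The CRF is not among the documents, and Table 1 shows no such item. Section 5.5 already assesses use at each contact, and 4.4.2 asks withdrawn women at 9 months about current use and expulsion. Without dates, end of use is known only to the interval between contacts. The LNG-IUS advantage may look smaller than under the present plan, by up to the unreplaced-expulsion rate.

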7.3 Subject Population(s) for Analysis

We will analyze all women randomized into the study, regardless of whether they received the study medications as an intention to treat analysis. In addition, we will analyze women who received at least one dose of TXA or had insertion of LNG-IUS, even if there was immediate expulsion.

8 Safety and Adverse Events

Adverse events would include perforation or embedment of the LNG-IUS. Adverse events will be recorded during the study by study coordinators or personnel and resolution of the AE reported, in particular if that required a second surgical procedure to resolve. Allergic reaction to either LNG or TXA will be collected and reported to the IRB per protocol. Worsening anemia or need for blood transfusion would be considered a safety endpoint.

8.1 Definitions

Unanticipated Problems Involving Risk to Subjects or Others (UPIRTSO)

Any unanticipated problem or adverse event that meets the following three criteria:

- **Serious:** Serious problems or events that results in significant harm, (which may be physical, psychological, financial, social, economic, or legal) or increased risk for the subject or others (including individuals who are not research subjects). These include: (1) death; (2) life threatening adverse experience; (3) hospitalization - inpatient, new, or prolonged; (4) disability/incapacity - persistent or significant; (5) birth defect/anomaly; (6) breach of confidentiality and (7) other problems, events, or new information (i.e. publications, DSMB reports, interim findings, product labeling change) that in the opinion of the local investigator may adversely affect the rights, safety, or welfare of the subjects or others, or substantially compromise the research data, **AND**
- **Unanticipated:** (i.e. unexpected) problems or events are those that are not already described as potential risks in the protocol, consent document, not listed in the Investigator's Brochure, or not part of an underlying disease. A problem or event is "unanticipated" when it was unforeseeable at the time of its occurrence. A problem or event is "unanticipated" when it occurs at an increased frequency or at an increased severity than expected, **AND**
- **Related:** A problem or event is "related" if it is possibly related to the research procedures.

Adverse Event

An untoward or undesirable experience associated with the use of a medical product (i.e. drug, device, biologic) in a patient or research subject.

Serious Adverse Event

Adverse events are classified as serious or non-serious. Serious problems/events can be well defined and include;

- death
- life threatening adverse experience
- hospitalization
- inpatient, new, or prolonged; disability/incapacity
- surgical intervention for complications
- ectopic pregnancy
- Pelvic inflammatory disease
- Venous thromboembolism

and/or per protocol may be problems/events that in the opinion of the sponsor-investigator may have adversely affected the rights, safety, or welfare of the subjects or others, or substantially compromised the research data.

All adverse events that do not meet any of the criteria for serious, should be regarded as **non-serious adverse events**.

Adverse Event Reporting Period

For this study, the study treatment follow-up period is defined as 9 months after enrollment. Events occurring after this visit will be managed clinically. For women with a contraindication to LNG-IUS (e.g. a type I fibroid), we will recommend removal of the LNG-IUS at the 9-month visit to reduce risks.

Preexisting Condition

A preexisting condition is one that is present at the start of the study. A preexisting condition should be recorded as an adverse event if the frequency, intensity, or the character of the condition worsens during the study period.

General Physical Examination Findings

At screening, any clinically significant abnormality should be recorded as a preexisting condition. At the end of the study, any new clinically significant findings/abnormalities that meet the definition of an adverse event must also be recorded and documented as an adverse event.

Post-study Adverse Event

All unresolved adverse events should be followed by the sponsor-investigator until the events are resolved, the subject is lost to follow-up, or the adverse event is otherwise explained. At the last scheduled visit, the sponsor-investigator should instruct each subject to report, to the sponsor-investigator, any subsequent event(s) that the subject, or the subject's personal physician, believes might reasonably be related to participation in this study.

Abnormal Laboratory Values

A clinical laboratory abnormality should be documented as an adverse event if hemoglobin were to drop below 8.0 g/dL during treatment for HMB.

Hospitalization, Prolonged Hospitalization or Surgery

Any adverse event that results in hospitalization or prolonged hospitalization should be documented and reported as a serious adverse event unless specifically instructed otherwise in this protocol. Any condition responsible for surgery should be documented as an adverse event if the condition meets the criteria for an adverse event.

Neither the condition, hospitalization, prolonged hospitalization, nor surgery are reported as an adverse event in the following circumstances:

- Hospitalization or prolonged hospitalization for diagnostic or elective surgical procedures for a preexisting condition. Surgery should **not** be reported as an outcome of an adverse event if the purpose of the surgery was elective or diagnostic and the outcome was uneventful.

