1.3 Clinical Data to Date

Several studies have shown good efficacy of both the LNG-IUS and TXA in the treatment of HMB in the presence of small uterine fibroids {Grigorieva, 2003 #1010} {Gupta, 2015 #992} {Lukes, 2010 #986}. We demonstrated in our large insurance-claims database that women with clinically significant fibroids were more likely to continue use of LNG-IUS (62% at 6 months) than TXA (22% at 6 months) for the treatment of HMB. No studies have demonstrated the reasons for discontinuation of treatment. A case report published after the start of this study shows intratumoral atherosclerosis-like vasculopathy in a fibroid treated with tranexamic acid; no side effects were noted in this case but surgery was done due to lack of response to TXA. The side effects and reasons for discontinuation noted thus far in our study include diarrhea, abdominal cramping, lack of effect, pelvic pain and dysmenorrhea.

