1.4 Dose Rationale and Risk/Benefits

Both medications are being used at the clinically acceptable dosages as indicated for the treatment of HMB. Risks of LNG-IUS related to fibroids include expulsion, perforation, or embedment of device. The risk of TXA related to fibroids is necrosis of the fibroids leading to pain.

2 Study Objectives

Primary Objective

To determine the comparative effectiveness [as measured by the Menorrhagia Multi-Attribute Scale (MMAS)] and duration of use of TXA versus LNG-IUS for the treatment of HMB in women with uterine fibroids.

Hypothesis: A user-independent medical therapy (LNG-IUS) will result in better patient reported outcomes and longer use compared to self-administered medication (TXA)

Secondary Objective

To determine the clinical and fibroid-related predictors of successful medical therapy of HMB in women with uterine fibroids.

Hypotheses: Large fibroid size will limit the effectiveness of LNG-IUS compared with TXA; elevated BMI predicts higher success with LNG-IUS over TXA.

[figure not shown]
3 Study Design

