4.1 Inclusion Criteria

- Premenopausal women aged 25-50
- Seeking treatment for HMB with a completed clinical evaluation
- Image-confirmed uterine fibroids of at least 1 cm in size and either submucosal or intramural
- Monthly menses
- Completed evaluation of HMB within one year
- Able to give consent for inclusion in the study
- Understands the English language for consent and questionnaires
- Self-reported HMB 3 months or more
- Not pregnant or breast-feeding

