4.4.2 Data Collection and Follow-up for Withdrawn Subjects

We will use the data obtained up until the person withdraws from the study, but will attempt to obtain permission for follow-up at 9 months for the subjects who have withdrawn. This endpoint will include whether the participant is still using either of the treatments, has any adverse events from treatment, had other procedures for HMB, and if there was expulsion of intrauterine device.

[figure not shown]
5 Study Drug

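### The elective-surgery exemption in 8.1 does not exclude fibroids or HMB, so elective surgery for the disease under study can go unreported as an AE or SAE

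*Combined protocol and SAP*

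**What the plan says.** All references are to the combined protocol and SAP.

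- **What counts as preexisting (8.1, Preexisting Condition).** "A preexisting condition is one that is present at the start of the study". A second rule follows: "A preexisting condition should be recorded as an adverse event if the frequency, intensity, or the character of the condition worsens during the study period".
- **Who enters (4.1).** One inclusion criterion is "Image-confirmed uterine fibroids of at least 1 cm in size and either submucosal or intramural"; another is self-reported HMB of three months or longer.
- **Hospitalization and surgery (8.1, Hospitalization, Prolonged Hospitalization or Surgery).** An AE that leads to hospital admission is an SAE unless the protocol instructs otherwise. The condition behind an operation is documented as an AE if it meets the AE criteria.
- **The exemption (same subsection).** "Neither the condition, hospitalization, prolonged hospitalization, nor surgery are reported as an adverse event in the following circumstances". One circumstance is listed: "Hospitalization or prolonged hospitalization for diagnostic or elective surgical procedures for a preexisting condition". The same bullet adds that elective or diagnostic surgery with an uneventful outcome is not to be reported as the outcome of an AE. The section does not define elective.
- **Use of the counts.** Under 8.4 the study team compares AEs and SAEs between the two arms and considers a hold if they differ. Under 8.5.1 the DSMB receives a summary of all AEs.
- **Other capture of procedures.** Section 4.4.2 asks at 9 months whether the woman "had other procedures for HMB", but only for withdrawn women who give permission. Table 1 schedules a medical records review in the 9-month column, which by its footnote also applies at withdrawal or termination.

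**The concern.** An exemption of this kind usually keeps unrelated, already planned operations out of the safety record. Here the preexisting condition is the disease under treatment, and elective surgery is a natural next step when medical therapy fails. Section 1.1 itself describes a high rate of surgical management, especially hysterectomy, in these women.

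A treatment effect can also act through the preexisting condition. Section 1.4 states: "The risk of TXA related to fibroids is necrosis of the fibroids leading to pain". Section 1.3 already lists pelvic pain, dysmenorrhea and lack of effect among the side effects and reasons for stopping seen in this study. If pain or bleeding worsens on treatment and the woman then has a scheduled operation, the rules in 8.1 give no clear answer on what is reported. At stake is whether such events reach the by-arm comparison behind the hold decision in 8.4 and the DSMB summary in 8.5.1.

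**Working it through.** The plan states no rate of surgery and no expected AE or SAE count, so there is no figure to reproduce. The check sets the rules side by side.

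**Step 1: does the exemption reach the study disease?** By the definition in 8.1, anything present at the start is preexisting. By 4.1, fibroids and HMB are present at the start in every eligible woman. The exemption carves out neither, so it reaches them.

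**Step 2: is it limited in another way?** It is limited to diagnostic or elective procedures. It is not limited to procedures planned before enrollment or to conditions that have not worsened.

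**Step 3: apply the rules case by case.**

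| Case during follow-up | Result under sections 8 and 8.1 |
|---|---|
| Elective surgery for fibroids or HMB that has not worsened | Exempt; neither AE nor SAE |
| Elective surgery after fibroids or HMB worsened | Conflict: the worsening rule requires an AE, while the exemption removes the condition, the stay and the operation |
| Non-elective surgery | Outside the exemption; documented if AE criteria are met, and an SAE if the AE led to admission |
| Surgery for a complication such as perforation or embedment | Reportable; surgery for complications is on the SAE list |
| Hemoglobin below 8.0 g/dL, worsening anemia or transfusion | Covered by separate rules, whatever surgery follows |

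**Step 4: resolve the second row in the most favorable way.** Suppose the worsening rule prevails and the worsened pain or bleeding is logged as an AE. The bullet still bars uneventful elective surgery from being reported as that AE's outcome, and the hospitalization rule yields to explicit protocol exceptions. The AE may then stay classed as non-serious despite an inpatient operation. Part of the loss survives this reading.

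**Step 5: does another route fill the gap?**
- Unanticipated-problem reporting (8.1) requires an event that is not part of an underlying disease, so it is unlikely to help.
- The procedure question in 4.4.2 is not stated for women who remain in the study.
- The discontinuation endpoint in 7.2 records that treatment was stopped or switched. It does not record the operation.
- The records review in Table 1 could supply the information, but no rule says that procedures are to be extracted or tabulated by arm.

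**The case against.** The strongest reply is that the gap is narrow and that most important events are caught elsewhere. Section 8.2 requires AEs to be sought by specific questioning at each contact, and all of them to be recorded. Worsening pain or bleeding would usually be logged before any scheduled operation, and nothing says that a later operation deletes the entry. Pain from drug-induced necrosis could also be viewed as a new event. Surgery for lack of effect alone is treatment failure, which the discontinuation endpoint would ordinarily pick up, so keeping it out of AE counts is defensible.

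Much of this stands. It does not remove the conflict in 8.1, whose exemption expressly covers the condition itself, and it does not restore the operation as an outcome of the AE.

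Four stronger inferences are tempting, and the documents do not support them:

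- **All surgery for fibroids or bleeding drops out.** Only diagnostic or elective procedures are exempt.
- **The exemption contradicts the SAE rule on hospitalization.** That rule expressly allows protocol exceptions, and this is one.
- **The case in 1.3 would have gone unreported.** The text says "surgery was done due to lack of response to TXA" and that no side effects were noted. It does not say that the surgery was elective.
- **The loss can be counted, and is larger with TXA.** Continued use at 6 months of 22% (TXA) and 62% (LNG-IUS) comes from insurance claims in which reasons for stopping were not known. It describes stopping, not surgery. Any count would need an assumed share of women going on to elective surgery, and the contrast between arms would follow from that assumption.

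**Conclusion.** The concern holds in limited form. As written, elective or diagnostic surgery for fibroids or HMB during follow-up can go unreported as an AE or SAE. For worsened disease, two rules in 8.1 conflict, and the operation is lost as an AE outcome even if the worsening is recorded. This is a defect in a stated rule, and it bears on the safety comparison in 8.4 and the summary to the DSMB.

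Its size in events and its direction between arms cannot be estimated from the documents. The conclusion rests on reading preexisting condition as 8.1 defines it, and elective in its ordinary sense of a scheduled procedure. It does not imply that the AE record as a whole is unreliable, or that a safety signal has been missed.

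**What to change.** 1. In 8.1, reconcile the two rules: limit the exemption to procedures planned before enrollment for a condition that has not worsened, and define elective.
2. State that surgery or hospitalization for worsened fibroids, bleeding or pelvic pain is classified by the existing AE and SAE definitions, and align the sentence on uneventful elective surgery with this.
3. Record every fibroid or HMB procedure during the 9 months, with its indication, in all women. Use the medical records review already in Table 1. For women who withdraw, that review may fall at withdrawal, so keep the 9-month question in 4.4.2; capture will stay incomplete for those who refuse permission.
4. Tabulate these procedures by arm for the DSMB, and show surgery for lack of effect alone separately from AEs so that treatment failure does not inflate the safety counts.

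The cost is amendment wording, a short addition to the CRF, one table, and a few more AE or SAE entries, some of which will reflect disease progression. No extra visit or test is needed.
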